Impact of Diabetes Mellitus on Retinal Microvasculature in Patients without Clinical Retinopathy Using Optical Coherence Tomography Angiography

Study Protocol Submitted for Partial Fulfillment
of Master Degree in ophthalmology

Presented by

[name]

M.B.B.CH

Resident of Ophthalmology
Sohag University Hospital.

Supervised by

[name]

Professor of Ophthalmology
Faculty of Medicine, Sohag University

[name]

Assistant Professor of Ophthalmology
Faculty of Medicine, Sohag University.

[name]

Lecturer of Ophthalmology
Faculty of Medicine, Sohag University.

Sohag University
2024

Introduction

Diabetic retinopathy (DR) is a common microvascular complication of diabetes mellitus (DM) and is the leading cause of preventable blindness in working aged people [1].

Fluorescein angiography (FA) is the gold standard investigation for evaluation of Diabetic Retinopathy, yet it is time-consuming and requires invasive intravenous dye administration that may cause various reactions such as vomiting and urticaria [2].

The advent of Optical Coherence Tomography Angiography (OCTA) overcame these disadvantages and added value of imaging rapid and high-resolution images of the retinal microvasculature without intravenous dye administration [3, 4].

OCTA identifies features of preclinical retinopathy that are not detectable by clinical examination and evaluates early ischemic changes as enlarged foveal avascular zones (FAZ) [5-8] , reduced vessel density [8, 9] that are reported to present without clinical retinopathy and also microaneurysm formation which is the most common early clinically visible manifestation of DR [10].

Duration of diabetes has been reported to be a strong predictor for the progression of DR as persistent elevated blood glucose level gradually leads to weakening of the walls of small retinal blood vessels leading to tiny bulges and even leakage [11, 12].

Aim of the work

To assess the impact of duration of DM on OCTA parameters in diabetic patients without clinical Diabetic retinopathy.

Patients and Methods

Study design: Observational, Cross-sectional study.

Study setting: Sohag University Hospital, department of Ophthalmology.

Study population: patients will be recruited from diabetics who will present for retinopathy screening examination at outpatient clinic of Sohag University Hospital.

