Sample size determination: every group would include from 60 to 80 eyes calculated by Yamane's formula: $n = N / (1 + N) e^2$, where n = the sample size, N = the population of the study and e = the margin error in the calculation.

The study will be conducted after acquiring the approval of the Medical Research Ethics Committee in the Faculty of Medicine, Sohag University considering that all study participants will be carefully cognized with the nature, presentation and potential consequences of the disease, investigation options and importance of regular follow up and tight control by an informed consent.

Inclusion criteria:

- 1) Age : Above 40 years old
- 2) Type of DM: Type 2.
- 3) Fundus examination: no macular edema or other signs of clinical retinopathy.

Exclusion criteria:

- 1) Age : below 40 years old
- 2) Ocular history : any history of significant ocular injury or disease that could affect the retinal microvasculature such as retinal vascular occlusion, glaucoma, or vitreo-macular disease, as such conditions have also been noted to show sub-clinical OCTA changes [13, 14].
- 3) Fundus examination: macular edema or any other signs of clinical retinopathy.

Procedure: patients recruited for the study will be subjected to the following:

- Personal history: including name, age, sex, occupation and residency.
- Medical history: including duration of DM, type of DM, use of DM medications, most recent hemoglobin A1C and presence of comorbid diseases.
- Ocular examination: including extra-ocular examination, anterior segment examination, visual acuity assessment, IOP measurement and posterior segment examination.

Signs of diabetic retinopathy to be detected include; Micro-aneurysm, Dot and Blot hemorrhages, Flame-shaped splinter hemorrhages, Retinal edema and hard exudates, Cotton-wool spots, venous loops and venous and Intra-retinal microvascular abnormalities (IRMA).

Patients who meet the inclusion criteria will be divided into three groups depending on the duration of diabetes: 0–5 years (short), 6–10 years (medium), and more than 10 years (long). Fourth control group of patients who meet the criteria and don't have DM will be included.

OCTA images will be obtained for the patients by a comprehensive wide-field OCT device (Optovue RTVue XR 100 Avanti, Germany) with 6×6 mm field of view centered at the fovea.

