One eye will be selected for inclusion from each patient. If both eyes from an individual patient are similar the right eye will be included in the study. The effect of eye motion-related artifacts is minimized using VTRAC eye tracking software [19].

Images to be included in the study will be required to have a signal strength greater than 7, minimal motion artifacts, decentralization from the foveal center of less than 20 μm , and minimal evidence of obscuration by media opacities [20].

Image analysis will be automatically performed by the AngioVue Comprehensive software, which will provide automated segmentation and calculation of retinal microvascular metrics such as FAZ-related and SVD. The analysis will include the inner retina between the inner limiting membrane and an anterior offset from the retinal pigment epithelium of 110 μm . The superficial capillary plexus (SCP) as the superficial 70% of the inner retina, and the deep capillary plexus (DCP) is the remaining 30% [21].

OCTA parameters derived from the SCP and DCP will be classified into two categories:

- (1) FAZ related metrics: FAZ area, FAZ perimeter and FAZ flow density (FD)
- (2) Vessel density-related metrics: superficial vessel density (SVD) and deep vessel density (DVD) in the 6 mm patch (6 mm diameter around the foveal center), 1 mm patch (1 mm diameter around the foveal center), and inner ring (1 mm patch excluding the FAZ) [9, 20].

Statistical Analysis

Statistical analysis will be performed using SPSS software 23 (SPSS, Inc., Chicago, IL, USA). The Shapiro–Wilk test will be used. Comparisons between groups will be made using the Kruskal–Wallis H test or one-way ANOVA test. Differences between two groups will be estimated with a Mann–Whitney U test or t-test. Multivariate linear regression models will be used to analyze potential associations between each OCTA parameter and systemic risk factors. All p values will be based on two-tailed testing and considered to be statistically significant if $p < 0.05$. A Bonferroni correction will be applied when appropriate.

References

- 2) Early Treatment Diabetic Retinopathy Study Research Group. Classification of Diabetic Retinopathy from Fluorescein Angiograms: ETDRS Report Number 11. *Ophthalmology* 1991, 98, 807–822.

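### The planned group comparisons cannot separate diabetes duration from age, and the plan does not tie its regression to duration, the only stated aim

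*Combined protocol and SAP*

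**What the plan says.** The section Aim of the work gives one aim: "To assess the impact of duration of DM on OCTA parameters in diabetic patients without clinical Diabetic retinopathy". The title is wider: "Impact of Diabetes Mellitus on Retinal Microvasculature in Patients without Clinical Retinopathy".

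Under Procedure, diabetic patients are placed in three duration bands: "0–5 years (short), 6–10 years (medium), and more than 10 years (long"). A non-diabetic group is added: "Fourth control group of patients who meet the criteria". Age and sex are recorded in the personal history ("including name, age, sex, occupation and residency"). The medical history records duration itself and also "most recent hemoglobin A1C and presence of comorbid diseases". No matching of groups on age is stated.

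The Statistical Analysis section offers three tools:

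- **Global test.** "Comparisons between groups will be made using the Kruskal–Wallis H test or one-way ANOVA test". The groups entering it are not listed, and none is excluded.
- **Two-group tests.** Mann–Whitney or t-test, with the pairs not named.
- **Linear regression.** Each OCTA parameter is related to systemic risk factors. The section does not say whether duration or age is among them, or whether controls are included.

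Significance is two-sided at 0.05, with Bonferroni where appropriate. No result is designated as the answer to the aim.

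**The concern.** Type 2 patients with more than ten years of diabetes may well be older than those diagnosed within five years. If OCTA measures change with age, the bands will differ even when duration does nothing. Kruskal–Wallis, ANOVA, Mann–Whitney and the t-test compare the bands as they stand, so none of them can separate the two explanations. The regression could, but as written nothing obliges it to contain duration or age.

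The second issue is the control group. If all four groups enter the global test, a significant result may reflect only diabetes versus no diabetes. That is a reasonable question, and the title suggests it may be of interest, but it is not the stated aim.

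At stake is whether a reported duration effect can be believed as one.

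**Working it through.** **Inputs from the document.** 60 to 80 eyes per group (Sample size determination); one eye per patient, so eyes equal patients; three duration bands plus controls; two-sided alpha 0.05. The sample size section gives no effect size, SD, or values for the inputs of its formula. The 60 to 80 therefore cannot be reproduced and is used here only as the group size.

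**Assumptions.** All effect sizes, in SD units, are assumed because the document gives none. Data are normal with SD 1 and equal groups. Paired figures are n=60 / n=80 per group.

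**1. Age effect only, no duration effect.** Let age alone shift the outcome linearly by d from the short to the long band.

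- Trend contrast (−1, 0, 1): noncentrality d√(n/2), with 3n−3 degrees of freedom. For d=0.2: 0.2×√30=1.095 and 0.2×√40=1.265.
- Three-band ANOVA: λ = n·d²/2. For d=0.2: 60×0.02=1.2 and 80×0.02=1.6.

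| Age-only shift d | Unadjusted trend rejects | Three-band ANOVA rejects |
|---|---|---|
| 0.1 SD | 8% / 10% | 7% / 8% |
| 0.2 SD | 19% / 24% | 15% / 19% |
| 0.3 SD | 37% / 47% | 29% / 37% |

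With age in the model, and age explaining 20% of the variation in the duration score, a simulation of 20,000 runs at d=0.2 gives 4.8% / 5.0%, the nominal level.

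**2. Controls differ, bands identical.** For a four-group ANOVA with controls d away, λ = n·d²·¾.

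- d=0.3: λ = 4.05 / 5.40; significant in 36% / 47%.
- d=0.5: λ = 11.25 / 15.0; significant in 81% / 91%.

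In the same setting (400,000 simulated runs), at least one diabetic–diabetic pair is falsely significant in about 2% with Bonferroni over all six pairs, and in about 12% without correction.

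**3. Price of adjustment.** Take a true linear duration effect of 0.5 SD from short to long. The unadjusted trend has noncentrality 0.5×√30=2.739 / 0.5×√40=3.162, so power is 78% / 88%. If the covariates explain a share R² of the duration score and none of the outcome, noncentrality is multiplied by √(1−R²).

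- R²=0.2: 2.449 / 2.828; power 68% / 80%.
- R² from 0.1 to 0.3: power 73% to 63% (n=60) and 85% to 75% (n=80).
- R²=0.2 with duration entered as three unordered bands: 58% / 71%.

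**4. Several parameters.** The OCTA list has at least nine: three FAZ metrics, plus two densities in three regions (3 + 2×3 = 9). Nine independent tests at 0.05 would give 1−0.95⁹ = 37% familywise error. At 0.05/9, the adjusted trend of step 3 (R²=0.2) has power 36% / 51%.

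**The case against.** The strongest defence is that the plan already holds the pieces. Three of the four groups are duration bands, pairwise tests and Bonferroni follow the global test, age is recorded, and a multivariable regression is planned in which duration and age could both appear. Much of this stands. A reader might infer that the plan has no test of duration, but the pairwise tests can supply one. Nor are the 36% to 91% in step 2 a false-positive rate: they are the power of a valid test of a different question, and corrected pairwise tests largely prevent it being taken for duration. That controls enter the global test is itself the natural reading, not a stated rule.

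A reader might also infer that an unordered test of ordered bands is an error. It is not. The document predicts no linear shape. The adjusted trend (68% / 80%) only matches the unadjusted three-band ANOVA (68% / 81%) for a linear 0.5 SD effect. If only the middle band differs by 0.5 SD, a trend finds it in 5% against 81% for ANOVA at n=60.

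The role of HbA1c is open too. The Introduction says "persistent elevated blood glucose level gradually leads to weakening of the walls of small retinal blood vessels", which makes glucose a possible route for the duration effect. However, only the most recent HbA1c is collected, and nothing shows how much of the effect it carries.

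The defence does not remove the age problem. Pairwise tests are as unadjusted as the global test, and a regression that could include duration and age is not one that will.

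**Conclusion.** The concern holds in this form: followed as written, the group comparisons cannot distinguish duration from age, and the one planned method that could is not directed at duration. At an assumed 0.2 SD age-only shift, false rejection is 15% to 24% depending on test and group size, against about 5% after adjustment. At 0.1 SD the excess is small; at 0.3 SD it is large. The size therefore rests on an age gradient across bands and an age effect on OCTA measures, neither of which the document quantifies. The 5% assumes that age acts linearly and is in the model.

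The control-group issue is secondary: a significant four-group result need not concern duration, but the pairwise tests partly guard against that. How duration is coded, whether comorbidities are adjusted for, where HbA1c is placed, and which result takes precedence are choices for the sponsor. They are not errors in the plan.

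**What to change.** Add to the Statistical Analysis section, before results are seen, wording to this effect:

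*The aim will be answered by linear regression in the diabetic patients only. For each OCTA parameter, diabetes duration will be the exposure and age and sex the covariates. The duration effect will be reported with its 95% confidence interval, and the Bonferroni correction will be applied across the OCTA parameters. Diabetic versus control will be reported as a separate comparison and will not be taken as evidence on duration.*

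The sponsor should also state the chosen coding of duration (ordered bands, separate bands or years). Adjustment for comorbidities, a sensitivity model with HbA1c, and a precedence rule between tests are optional.

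**Cost.** No new data are needed: duration, age and sex are already collected. Under the step 3 assumptions (20% of the duration score explained), adjustment takes power from 78% to 68% at n=60 and from 88% to 80% at n=80. Correction over nine parameters brings the adjusted figures to 36% and 51%. That second drop comes from the multiplicity correction, and the same correction would also lower the power of the unadjusted tests.

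### The stated tests of diabetes duration are unadjusted and the planned regression is not tied to the aim, so an age difference between groups could be reported as a duration effect

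*Combined protocol and SAP*

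**What the plan says.** The Aim of the work section states one question: "To assess the impact of duration of DM on OCTA parameters in diabetic patients without clinical Diabetic retinopathy". Patients and Methods gives the design: "Study design: Observational, Cross-sectional study". The Procedure section forms three diabetic groups by years since onset (0–5, 6–10, more than 10) and adds a non-diabetic control group. On age, the criteria set a floor, "Age : Above 40 years old"; no upper limit, matching or stratification is stated. On size, "every group would include from 60 to 80 eyes", and "One eye will be selected for inclusion from each patient", so eyes and patients coincide.

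Statistical Analysis states two kinds of group test. For several groups: "Comparisons between groups will be made using the Kruskal–Wallis H test or one-way ANOVA test". For pairs: "Differences between two groups will be estimated with a Mann–Whitney U test or t-test". It then adds: "Multivariate linear regression models will be used to analyze potential associations between each OCTA parameter and systemic risk factors". The covariates of that model are not listed, neither duration nor age is named, and it is not linked to the aim. Tests are two-sided at 0.05, with a Bonferroni correction left to judgement.

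**The concern.** Nothing in the design balances the duration groups on age. People who have had diabetes for more than ten years may well be older than those diagnosed within five; the documents do not say so, and it is an assumption here. If they are older, and if an OCTA parameter varies with age, the group tests will show a difference even when duration has no effect. The reader of the results could not tell the two apart.

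The regression could separate them, but nothing commits it to do so. Nor does the plan say which result prevails if a group test is significant and the regression is not. With several FAZ and vessel-density parameters, a covariate set chosen after the data are seen could decide the conclusion.

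**Working it through.** The plan gives no figure on this point to reproduce. The check shows how far an age difference alone can move the stated tests.

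**Inputs from the documents.** 60 or 80 eyes per group, one per patient; two-sided 0.05; four groups, hence 6 pairs.

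**Assumed inputs.** Within-group age SD 8 years; long-minus-short gap in mean age 4 to 8 years (middle 6); within-group age–OCTA correlation r of 0.2 to 0.4 (middle 0.3); medium group halfway in age; linear age effect; no true duration effect.

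**Step 1: spurious difference.** In outcome SDs, d = r × gap / 8.
- Low: 0.2 × 4/8 = 0.10
- Middle: 0.3 × 6/8 = 0.225
- High: 0.4 × 8/8 = 0.40

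**Step 2: rejection rates.** Long versus short uses the noncentral t with 2n − 2 degrees of freedom and noncentrality d × √(n/2); in the middle case with n = 60 this is 0.225 × √30 = 1.23. The three-group ANOVA uses the noncentral F with means 0, d/2, d. Each cell gives n = 60 / n = 80.

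| Case | d | t-test, 0.05 | t-test, 0.05/6 | ANOVA, 0.05 |
|---|---|---|---|---|
| Low | 0.10 | 8.4% / 9.6% | 1.9% / 2.3% | 7.3% / 8.1% |
| Middle | 0.225 | 23.1% / 29.3% | 7.7% / 10.9% | 17.8% / 22.6% |
| High | 0.40 | 58.4% / 71.0% | 31.6% / 44.6% | 48.0% / 60.8% |
| Nominal | 0 | 5% | 0.8% | 5% |

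Mixed cases fall between: an 8-year gap with r = 0.2, or a 4-year gap with r = 0.4, both give d = 0.20 and t-test rates of 19.2% / 24.2%. The rate rises with n, so more eyes do not help. Bonferroni lowers the rates but leaves d unchanged.

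**Step 3: with adjustment.** All 18 combinations (gap 4, 6, 8; r 0.2, 0.3, 0.4; n 60, 80) were simulated with 10,000 runs each. Sex was unrelated to group and outcome. The unadjusted t-test rejected in 8.6% to 71.6% of runs; the model with age and sex rejected in 4.4% to 5.2%.

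**Step 4: precision.** The ratio of adjusted to unadjusted standard error for long versus short is √[(1 − r²)(1 + g²/6)], with g = gap/8.
- Gap 4, r 0.4: √(0.84 × 1.0417) = 0.935
- Gap 6, r 0.3: √(0.91 × 1.09375) = 0.998
- Gap 8, r 0.2: √(0.96 × 1.1667) = 1.058

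**The case against.** The strongest reply is that the plan already contains an adjusted analysis. The Introduction calls duration a strong predictor of progression, the Procedure section collects age, duration, HbA1c and comorbid disease, and the regression may well be meant to include them. On that reading the gap is one of specification. This is fair as far as it goes: the plan does not exclude adjustment. But it does not promise it either, and the only tests that it assigns to comparing groups are unadjusted.

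The size can also be disputed. A 2-year gap with r = 0.2 gives d = 0.05 and a rejection rate of only 5.8% (n = 60) or 6.1% (n = 80). If the pairwise test is run only after a significant four-group ANOVA, with controls assumed midway in age, the middle case falls to about 12% and 16%, or 7% and 10% with Bonferroni. Both points stand. They show that the size depends on unknown ages and on the order of testing; they do not remove the bias.

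Finally, making linear regression the main analysis gives up the rank tests foreseen for skewed parameters. In a simulation with a skewed outcome, the model with age and sex rejected in 5.1% of runs against 23.7% unadjusted, so skewness alone is not a reason to avoid it. Checking residuals remains sensible.

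**Conclusion.** The concern holds. As written, the stated comparison of duration groups carries any age difference between them, and no text makes an age-adjusted estimate of duration the answer to the aim. The size cannot be known from the documents. Under the assumed middle case, the uncorrected long-versus-short t-test rejects about five times as often as its nominal 5%; near the mild end the excess is slight. These rates apply to the unadjusted tests only, not to a regression that includes age. The point should be fixed before analysis. It does not invalidate the study. Confidence is medium, because the direction and size of any age imbalance are assumed.

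**What to change.** State in Statistical Analysis that the main analysis for the aim is the linear regression of each OCTA parameter on duration group, fitted in the diabetic patients, with age and sex as prespecified covariates. In addition:

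- Report adjusted differences with 95% confidence intervals, tabulate age by group, and label the unadjusted tests as descriptive.
- Show results with and without HbA1c, and with and without comorbid disease, as sensitivity analyses. Either may lie on the pathway from duration, so neither belongs in the main model by default.
- Adjust the comparison of diabetic patients with controls for age and sex as well, in a separate model without duration.

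**Cost.** A few lines of text and no new data. Age and sex use two degrees of freedom: 3 × 60 − 5 = 175 residual instead of 177, or 3 × 80 − 5 = 235 instead of 237. The standard error of the long-versus-short difference changes by roughly −6% to +6% under the assumed ranges; the increase comes when the age gap is large and the correlation weak. Comorbid disease needs a fixed coding, since the plan does not define it. Patients without a recent HbA1c drop out of that sensitivity version only. If the age gap proves large, the adjusted estimate leans on a roughly linear age effect, and the report should say so.

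### Does the undefined scope of the Bonferroni correction, with no primary OCTA parameter or contrast named, call for a change to the plan?

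*Combined protocol and SAP*

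**What the plan says.** The aim (Aim of the work) is the effect of diabetes duration on OCTA parameters as a set; no single one is picked out. The Procedure section forms three duration groups (0–5, 6–10 and more than 10 years) and adds a control group without diabetes. Sample size determination gives 60 to 80 eyes per group.

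The parameter list just before Statistical Analysis has two parts. One is FAZ area, perimeter and flow density. The other begins "Vessel density-related metrics: superficial vessel density (SVD) and deep vessel density (DVD) in the 6 mm patch" and goes on to the 1 mm patch and the inner ring.

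Statistical Analysis then runs in this order:

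- a Kruskal–Wallis test or one-way ANOVA across groups;
- two-group tests: "Differences between two groups will be estimated with a" Mann–Whitney or t-test;
- regression: "Multivariate linear regression models will be used to analyze potential associations between each OCTA parameter and systemic risk factors";
- a two-tailed significance level of 0.05 for all p values;
- finally, "A Bonferroni correction will be applied when appropriate".

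The section does not say which tests form the Bonferroni family, what triggers the correction, or whether the 0.05 level applies to raw or adjusted p values.

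**The concern.** With several parameters, several pairs of groups and no stated family, the same p value can be called significant or not according to a divisor that could be settled after the results are seen. A raw p of 0.02 meets the 0.05 level but fails Bonferroni over only three pairs (0.0167). A raw p of 0.005 passes Bonferroni over the six pairs of one parameter and fails it over all pairs of all parameters.

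Any of nine parameters and any of three duration pairs could supply a positive finding on the aim. If correction is confined to pairs within a parameter, nothing adjusts for the number of parameters. What is at stake is whether a reported effect of duration carries the error rate that a reader would assume from the 0.05 level.

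**Working it through.** The plan states no family size, so there is no figure of its own to reproduce. The inputs are its counts, its 0.05 two-sided level and its 60–80 eyes per group.

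**1. Number of tests.** Parameters: 3 FAZ + 2 plexuses × 3 regions = 9. If the FAZ metrics are taken in each plexus, 6 + 6 = 12. Pairs among four groups: 4 × 3 / 2 = 6, of which 3 compare duration groups. Duration tests: 9 × 3 = 27. All pairwise tests: 9 × 6 = 54, or 12 × 6 = 72.

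**2. Threshold, observed difference needed, and power.** Threshold = 0.05/k. Critical observed difference at n = 70 per group = t(1 − 0.05/(2k), 138) × √(2/70), with √(2/70) = 0.169. Power is for a two-sample t-test with an assumed true difference of 0.5 SD.

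| Divisor k | Threshold | Critical difference, n = 70 | Power, n = 60 to 80 |
|---|---|---|---|
| 1 | 0.05 | 1.977 × 0.169 = 0.334 SD | 78–88% |
| 6 | 0.0083 | 2.677 × 0.169 = 0.452 SD | 52–69% |
| 27 | 0.00185 | 3.174 × 0.169 = 0.537 SD | 33–50% |
| 54 | 0.00093 | 3.385 × 0.169 = 0.572 SD | 26–42% |

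With 72 tests the threshold is 0.0007. At n = 70, an observed difference between 0.45 and 0.57 SD passes with divisor 6 and fails with divisor 54.

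**3. False duration findings.** Simulation of 10,000 studies per setting: four groups of 70, nine normal parameters, t-tests, no duration effect. The documents give no correlations, so equal correlations from 0 to 0.95 are assumed. Chance of at least one significant result among the 27 duration tests:

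| Correlation | 0 | 0.5 | 0.8 | 0.9 | 0.95 |
|---|---|---|---|---|---|
| No correction | 69% | 54% | 35% | 28% | 22% |
| Divisor 6 | 19% | 14% | 9% | 7% | 5% |
| Divisor 54 | 2.6% | 2.2% | 1.4% | 0.9% | 0.8% |

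With assumed correlations of 0.9 within the FAZ, SVD and DVD blocks and 0.3 between them, the figures are 11% (divisor 6) and 1.5% (divisor 54). Requiring a significant four-group ANOVA first changes the divisor-6 row little: 17% to 5% when the controls equal the diabetic groups.

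**4. How often the divisor matters.** Take the verdict to be whether any of the 27 duration tests is significant. Divisors 6 and 54 then disagree in 16% (correlation 0) to 4% (0.95) of studies with no effect. With an assumed long-minus-short difference of 0.3 SD in all nine parameters they disagree in 43% to 21%. At 0.5 SD the pattern reverses: 2% at correlation 0, rising to 27% at 0.95.

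**5. What a pairwise family leaves out.** Nine omnibus tests at 0.05 give at least one false positive with probability 1 − 0.95⁹ = 37% if independent, falling to 10% at correlation 0.95 (simulated, global null). The regressions come on top. Even a divisor of 54 therefore does not cap the error of everything planned.

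**6. What a single primary t-test would not cure.** Duration groups may differ in age or other factors. If such differences shifted the long-versus-short comparison by an assumed 0.1, 0.2 or 0.3 SD, an unadjusted t-test at 0.05 with n = 70 would reject in 9%, 22% or 42% of studies with no duration effect.

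**The case for a change.** The strongest case for a change is that the repair is only wording, needs no extra eyes, and could be made before image analysis. The plan does not call itself exploratory; it sets a significance level for all its p values. The within-parameter reading is customary but not written, and it leaves the nine parameters uncorrected: 9–19% for correlations of 0.8 down to 0, and 11% under the block pattern. No omnibus gate is stated, and a gate would help little. One named primary comparison would have 78–88% power for 0.5 SD at a clear 5% level.

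Much of this stands. The family is undefined, the arithmetic is right, and the within-parameter reading reaches 5% only when the parameters are almost perfectly correlated.

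Two parts do not carry through. First, the 0.05 level and the Bonferroni sentence do not contradict each other: they fit together if adjusted p values are compared with 0.05. Second, the repair is not free. A single long-versus-short t-test takes the medium group out of confirmatory inference. It also puts an unadjusted comparison ahead of the regression, the only planned analysis able to account for other factors. The choice of parameter would be debatable too: the software-output phrase "retinal microvascular metrics such as FAZ-related and SVD" favours neither kind of metric. Holm over 27 keeps every parameter, but at the power shown above.

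**Conclusion.** The omission is real, but it is one that analysts ordinarily fill sensibly, and closing it more tightly is a trade-off with no clear gain. The sequence of omnibus test, two-group test and Bonferroni reads naturally as a post-hoc correction within each parameter (divisor 6, threshold 0.0083). Nothing in the text points to 54 or 72 in particular.

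On that reading the chance of a false duration contrast somewhere among 27 is about 5–19%, set almost entirely by the assumed correlation. Some positive correlation is plausible, because the regions are nested ("inner ring (1 mm patch excluding the FAZ") and the FAZ metrics describe the same structure, but the documents give no value. The low end of the range cannot be claimed as fact. The omnibus tests and regressions add to these rates under any pairwise divisor.

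The aim concerns a set of parameters and defines no single yes-or-no result, so a study-wide verdict on any one of 27 tests is a construct laid over the plan. For a cross-sectional master's thesis, results by parameter with within-parameter correction are a defensible choice. No change to the plan is called for on this point. A positive finding on one parameter out of nine should be read with the error range above in mind.
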